Includes standard therapy prescribed to the patient depending on the clinical picture of the disease and symptomatology.

The investigational therapy is assigned to the patient according to the results of the randomization procedure.

Visit 2 (day 11/12¹ from the start of therapy, Visit procedures are performed at the end of parenteral therapy):

Physical examination, neurological examination, assessment of vital signs (BP, HR, RR, body temperature), assessment of concomitant therapy, registration of AE and assessment of exclusion criteria, clinical and biochemical blood tests, urinalysis, ECG, completion of specialised scales and calculation of indices (mRS, NIHSS, HADS, MoCA, Rivermead mobility index), dispensing of oral medication.

Telephone call 1 (Day 24±2 from initiation of therapy; Day 14±2 from initiation of oral therapy): assessment of concomitant therapy, recording of AE and assessment of exclusion criteria, assessment of compliance.

Visit 3 (Day 40 (+2) from initiation of therapy; Day 30 (+2) from initiation of oral therapy): physical examination, assessment of vital signs (BP, HR, RR, body temperature), assessment of concomitant therapy, recording of AE and assessment of exclusion criteria, dispensing/administration of oral medication, assessment of compliance.

Telephone call 2 (Day 55±2 from initiation of therapy; Day 45±2 from initiation of oral therapy): assessment of concomitant therapy, recording of AE and assessment of exclusion criteria, and assessment of compliance.

Visit 4 (day 71(+2) from the start of therapy; end of therapy): physical examination, neurological examination, assessment of vital signs (BP, HR, RR, body temperature), assessment of concomitant therapy, registration of AE and assessment of exclusion criteria, clinical and biochemical blood tests, general urinalysis, pregnancy test for women with preserved reproductive potential, ECG, completion of specialised scales and calculation of indices (mRS, NIHSS, HADS, MoCA, Rivermead mobility index), return of the IP and assessment of compliance.

Additional in-person/out-person (phone calls) visits may be conducted if necessary, in the reasonable judgement of the investigator, particularly to monitor the progression of SAEs. The scope of activities and procedures performed at additional visits will be determined by the investigator on an individual basis, depending on the indications.

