Therapy period

Visit 2 (day 11/12³ from the start of therapy, Visit procedures are performed at the end of parenteral therapy)

The visit is conducted in the inpatient setting of the investigational site and includes the following procedures:

- physical examination,
- neurological examination,
- assessment of vital signs (BP, HR, respiratory rate, body temperature),
- evaluation of concomitant therapy,
- AEs registration;
- evaluation of exclusion criteria;
- clinical blood test,
- blood chemistry;
- urinalysis;
- ECG
- completion of specialised scales and calculation of indices (mRS, NIHSS, HADS, MoCA, Rivermead mobility index),
- dispensing of oral medication

The investigator decides on the patient's discharge from the hospital, instructs the patient on the rules of the trial, administration of the investigational therapy and planned Visits/procedures.

Telephone visit 1 (Day 24±2 from initiation of therapy; Day 14±2 from initiation of oral therapy).

¹ If data are available for a patient from instrumental examinations performed within 48 hours prior to inclusion in the trial, they can be used to assess the patient's condition and eligibility for inclusion/non-inclusion. The use of such data shall be permitted only if the data are available in full and for all parameters required by the Protocol.

² The plan is to use data from neuroimaging examinations performed within 48 hours prior to patient inclusion in the trial to assess patient status and eligibility for inclusion/non-inclusion. A repeat CT/MRI scan is not required if these findings are present.

³ If the first administration of the investigational product (start of parenteral therapy) falls on the second half of the day (first day of therapy - one administration), Visit 2 is performed on day 12 in the morning.

The investigator should contact the patient by telephone to assess concomitant therapy, to record AE and assess exclusion criteria, and to assess compliance.

Visit 3 (Day 40 (+2) from initiation of therapy; Day 30 (+2) from initiation of oral therapy):

The visit is conducted in the context of the patient's outpatient visit to the investigational site and includes the following procedures:

- physical examination,
- assessment of vital signs (BP, HR, respiratory rate, body temperature),
- evaluation of concomitant therapy,
- AEs registration;
- evaluation of exclusion criteria;
- dispensing/accounting for oral medication,
- compliance assessment

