Telephone visit 2 (Day 55±2 from initiation of therapy; Day 45±2 from initiation of oral therapy):

The investigator should contact the patient by telephone to assess concomitant therapy, to record AE and assess exclusion criteria, and to assess compliance.

Visit 4 (day 71(+2) from start of therapy; end of therapy)

The visit is conducted in the context of the patient's outpatient visit to the investigational site and includes the following procedures:

- physical examination,
- neurological examination,
- assessment of vital signs (BP, HR, respiratory rate, body temperature),
- evaluation of concomitant therapy,
- AEs registration;
- evaluation of exclusion criteria;
- clinical blood test,
- blood chemistry;
- urinalysis;
- pregnancy test for women with preserved reproductive potential,
- ECG
- completion of specialised scales and calculation of indices (mRS, NIHSS, HADS, MoCA, Rivermead mobility index),
- IP take-back and compliance assessment

Additional in-person/out-person (phone calls) visits may be conducted if necessary in the reasonable judgement of the investigator, particularly to monitor the progression of SAEs. The scope of activities and procedures performed at additional visits will be determined by the investigator on an individual basis, depending on the indications.

In case of early withdrawal of a patient from the trial, a Visit to End Patient Participation in the Trial is performed, including activities identical to those of Visit 4.

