7.1. Efficacy parameters under trial

According to the purpose and objectives of the present trial, the efficacy of the investigational product vs. comparator product will be assessed by the following parameters:

Primary efficacy criterion:

- The magnitude of change in the patient's **mRS** (Modified Rankin Scale) score at the end of therapy vs. baseline (in points).

Secondary efficacy criteria:

- The magnitude of change in the patient's **mRS** (Modified Rankin Scale) score at the end of parenteral therapy vs. baseline (in points).
- Proportion of disabled patients (**mRS** score 3 or more) at the end of therapy;
- Proportion of disabled patients (**mRS** score 3 or more) at the end of parenteral therapy;
- Proportion of patients with mRS score 0-1 at the end of therapy;
- Proportion of patients with mRS score 0-1 at the end of parenteral therapy;
- The magnitude of change in the patient's **NIHSS** (National Institutes of Health Stroke Scale) score at the end of therapy vs. baseline (in points).
- The magnitude of change in the patient's **NIHSS** (National Institutes of Health Stroke Scale) score at the end of parenteral therapy vs. baseline (in points).
- The magnitude of change in the patient's **MoCA** cognitive status score at the end of therapy vs. baseline (in points).
- The magnitude of change in the patient's **MoCA** cognitive status score at the end of parenteral therapy vs. baseline (in points).
- The magnitude of change in the patient's **Rivermead** Mobility Index score at the end of therapy vs. baseline (in points).
- The magnitude of change in the results of the patient's state assessment by the **Rivermead** mobility index at the end of the parenteral course of therapy vs. baseline (in points).
- The magnitude of change in the patient's **HADS** score at the end of therapy vs. baseline (in points).
- The magnitude of change in the patient's **HADS** score at the end of parenteral therapy vs. baseline (in points).

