Patient group	Group	$\mu \pm SD$	Efficacy evaluation:	
			95% CI for the difference in mean ($\mu_{\text{Mex.}} - \mu_p$)	Comparison between groups
ITT population (n = 144)	Group I (Mexidol®, n = 72)	2.278 ± 0.755	DM = 0.292 (0.027; 0.556)	p = 0.029 (Mann-Whitney U-test)
	Group II (Placebo, n = 72)	1.986 ± 0.847		

According to the results of the EPICA clinical trial, the mean value of the change in the mRS score at the end of the course of therapy relative to the baseline level in the group of therapy with the investigational product was (mean (SD)) 2.278 (0.755) points, in the placebo group - 1.986 (0.847) points 2.278 (0.755) points, in the group of placebo therapy - 1.986 (0.847) points, the difference (Mexidol® - placebo) is 0.292 points, 95% confidence interval for the difference (Mexidol® - placebo) is (0.027, 0.556). The "superiority" boundary (δ) was chosen as the lower boundary of the confidence interval constructed for the difference (Mexidol® - placebo). Thus, $\delta = 0.027$ points.

To test the hypothesis of "superiority" of therapy with the investigational product compared with placebo therapy **at a significance level of $\alpha = 0.05$ (5%) to ensure power $1-\beta = 0.8$ (80%)**, the sample size was calculated for the primary efficacy criterion given the parallel design, a 1:1 randomization scheme (i.e., $k = 1$ - the ratio of sample sizes of the groups n_T/n_p), the expected difference in efficacy between the compared products $\varepsilon = 0.292$ and with a mixed standard deviation (SD) of the in-group efficacy $\sigma = 0.802$ points.

The formula [Chow Sh.-Ch., Shao J., Wang H., 2008] was used in the calculation:

$$n_T = n_R \frac{\frac{(1 + 1/k) * (z_\alpha + z_\beta)^2 * \sigma^2}{(\varepsilon - \delta)^2}}{\frac{2 * (1.6449 + 0.8416)^2 * 0.802^2}{(0.292 - 0.027)^2}} \approx 114 \text{ people/gr,}$$

where z_α and z_β - quantiles of the normal distribution $N(0,1)$ (mean: 0, standard deviation: 1).

The minimum number of patients completing the trial in accordance with the protocol must be at least $N = 2 * 114 = 228$ patients (114 patients per group).

Given the possible attrition of patients in the trial, it is planned to **randomize 304 patients**, of whom **at least 228 should complete the trial according to the Protocol**.

Given the potential dropout of patients during the Screening phase, approval is planned for a clinical trial with a total of **336 screened patients**.

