9.6. Population to be analysed

The following population groups will be used for the analyses:

1. The ITT (Intent-to-treat) population will include all randomized patients regardless of investigational product/placebo administration.
2. The mITT (modified Intent-to-treat) population will include patients who have completed the full course of therapy, regardless of the presence of Protocol violations/ deviations.
3. The PP (Per protocol) population will include patients who completed the trial in accordance with the Protocol.

At the stage of statistical data processing, additional analyses of the efficacy and/or safety of investigational product/placebo in subpopulations of patients of different age groups can be performed.

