9.7.2. Statistical methods for assessing efficacy

The primary population for the evaluation of efficacy criteria, proof of the hypothesis of superiority of the trial drug therapy over placebo based on the primary efficacy criterion score,

will be the PP population.

Additionally, efficacy criteria will be analysed in the ITT and mITT populations.

This approach in selecting the population for analysis is based on the design of the planned clinical trial: patients in both the investigational product and placebo groups will receive standard (baseline) therapy (according to the Clinical Guidelines "Ischaemic Stroke and Transient Ischaemic Attack in Adults", 2015) with proven efficacy. Therefore, the use of the ITT population for a more conservative assessment of ongoing therapy is inappropriate, as this approach markedly offsets the clinical effects of the investigational product. Therefore, to compensate for the therapeutic effects of baseline therapy and to properly evaluate the effects of IP, the PP population is considered as the primary population for analysing efficacy parameters in the planned trial.

The trial plans to test the hypothesis of "superiority" of therapy with the investigational product vs. placebo therapy. The following indicator was chosen as the primary efficacy criterion: "The magnitude of change in the patient's **mRS** (Modified Rankin Scale) score at the end of therapy (Day 71) relative to baseline (in points)".

In the case of a superiority trial, the null hypothesis (H_0) and the alternative hypothesis (H_1) are formulated as follows:

$$H_0: \varepsilon = \mu_T - \mu_p \leq \delta, \quad H_1: \varepsilon > \delta, \quad \delta > 0, \text{ where}$$

- ε is the true difference between the value of the primary efficacy index (μ_T) in the group of patients taking the investigational product (T) and the value of the primary efficacy index (μ_p) in the group of patients taking placebo,
- δ - the boundary of "superiority" of therapy with the investigational product compared to placebo therapy by the primary efficacy indicator.

To prove superiority of therapy with the investigational product compared to placebo therapy, the lower bound of the 95% (or 97.06% in the case of a phase II trial) one-sided confidence interval (CI) for the difference in values of the primary efficacy criterion ($\mu_T - \mu_p$) must be greater than δ , where $\delta > 0$, i.e. CI must fall within the interval $(\delta, +\infty)$.

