Clinical laboratory assessments will be presented with descriptive statistics by trial visit indicating changes from baseline. Laboratory abnormalities outside of normal values will be noted. Lists and summary descriptions of clinically significant haematological laboratory abnormalities will be presented. The feasibility of using a number of statistical methods will be assessed after data collection has been completed, as the nature of the data distribution, sample homogeneity, etc. is not known in advance. During the course of the analysis, the list of methods to be used may be modified and supplemented if necessary for the qualitative processing of the data. All deviations from the statistical plan of the survey as well as their causes will be detailed in the statistical report.

Based on the results of the trial, after the final statistical analysis, a conclusion will be made about the efficacy and safety of different dosages in sequential therapy with Mexidol® solution for intravenous and intramuscular administration, 50 mg/ml (RPC PHARMASOFT LLC, Russia) and Mexidol® FORTE 250 film-coated tablets, 250 mg (RPC PHARMASOFT LLC, Russia), vs. placebo. Table templates are provided in the annexes to this statistical plan.

11. Patient populations to be analysed

The following population groups will be used for the analyses:

- The ITT (Intent-to-treat) population will include all randomized patients regardless of investigational drug/placebo administration.
 - The mITT (modified Intent-to-treat) population will include patients who have completed the full course of therapy, regardless of the presence of Protocol violations/ deviations.
 - The PP (Per protocol) population will include patients who completed the trial in accordance with the Protocol.
- **Subpopulation of patients involved in the evaluation of the pharmacodynamic effects of the investigational therapy:** this population will include PP patients with relevant blood test results.

The primary population for the evaluation of efficacy criteria, proof of the hypothesis of

Version 1.0 of 12.11.2021

Plan for statistical analysis of efficacy and safety parameters

superiority of the investigational product therapy over placebo based on the primary efficacy criterion score, will be the PP population. Additionally, efficacy criteria will be analysed in the ITT and mITT populations. Safety parameters will be analysed in the ITT population.

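### The Day 11/12 secondary endpoints take as their main analysis set patients who complete the trial per protocol to Day 71, so events in the tablet phase decide whose infusion-phase results count

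*Protocol*

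**What the plan says.** Protocol 7.1 lists 13 secondary endpoints. Seven are set at the end of the infusion course: change in mRS, mRS of 3 or more, mRS 0-1 ("Proportion of patients with mRS score 0-1 at the end of parenteral therapy"), and change in NIHSS, MoCA, Rivermead index and HADS. The SAP, written for protocol version 1.3, lacks the two mRS 0-1 items and so has six such endpoints of 11.

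These endpoints are measured at Visit 2, Day 11/12: "Visit procedures are performed at the end of parenteral therapy" (Protocol 6.1). All five scales are collected there: "completion of specialised scales and calculation of indices (mRS, NIHSS, HADS, MoCA, Rivermead mobility index" (Protocol 6.2). The trial ends about 60 days later: "Visit 4 (day 71(+2) from start of therapy; end of therapy".

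Protocol 9.6 defines the main set: "The PP (Per protocol) population will include patients who completed the trial in accordance with the Protocol". Protocol 9.7.2 introduces it with "The primary population for the evaluation of efficacy criteria, proof of the hypothesis of superiority" and closes by making PP primary for efficacy parameters in general. SAP 6 calls PP the main population for the efficacy analyses, and SAP 11 repeats the rule ("The primary population for the evaluation of efficacy criteria, proof of the hypothesis of"). ITT and mITT are additional. Neither document sets a different population for the Visit 2 endpoints.

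**The concern.** An endpoint at Day 11/12 is complete once Visit 2 is done. Making trial completion a condition for its main analysis selects patients on what happens to them afterwards. Protocol 5.3 allows exclusion at any time for, among others, recurrent stroke, adverse events, loss of contact or a positive SARS-CoV-2 test. Protocol 11.8 counts a prohibited drug or skipped visits as major deviations. Any of these can occur in the tablet phase, after the infusion course was given and assessed exactly as planned.

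This is a different question from whether PP suits the Day 71 primary endpoint. Here nothing is missing at the endpoint's own time point. The reason Protocol 9.7.2 gives for PP, that baseline therapy dilutes the effect, does not explain why a Day 11/12 result should depend on reaching Day 71. At stake are some precision in every case where patients are lost after Visit 2, and bias if that later loss is related to Day 11/12 status and differs between arms.

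**Working it through.** **The plan's own figures.** Inputs from Protocol 9.1: expected difference 0.292, margin 0.027, SD 0.802, one-sided alpha 0.05, power 80%.

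- n per group = 2 × (1.6449 + 0.8416)² × 0.802² / (0.292 − 0.027)² = 113.3, rounded up to 114. Two groups give 228, as stated.
- 228 / (1 − 0.25) = 304, as stated. The plan therefore allows 304 − 228 = 76 patients (25%) outside PP; of those randomised, "at least 228 should complete the trial according to the Protocol".

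**Who keeps a complete Visit 2 result after a tablet-phase event.**

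| Event after Visit 2 | PP (main) | mITT | ITT |
|---|---|---|---|
| Withdrawn or excluded, course not finished | out | out | in |
| Major deviation, course finished | out | in | in |

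ITT is all randomised patients, and Protocol 9.4 fills in no missing values. At Visit 2, ITT is therefore in effect all randomised patients with a Visit 2 value.

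**Precision.** The documents do not say how many of the 76 are lost after Visit 2, so the share is an assumption shown over its full range. The standard-error ratio is sqrt((228 + k)/228), where k is the number of observed Visit 2 results left out of PP.

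| Share of the 76 with Visit 2 data | k | Share of available results left out | SE ratio |
|---|---|---|---|
| 0% | 0 | 0% | 1.00 |
| 25% | 19 | 7.7% | 1.04 |
| 50% | 38 | 14.3% | 1.08 |
| 75% | 57 | 20.0% | 1.12 |
| 100% | 76 | 25.0% | 1.15 |

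In the sponsor's earlier phase III trial (Protocol 2.3.2), 124 of 150 randomised patients were in the per-protocol efficacy set, a loss of 26/150 = 17.3%. At that rate about 53 of 304 would fall outside PP, and the ratio is at most sqrt(150/124) = 1.10.

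**Bias.** Assume that later loss falls on patients with less Day 11/12 improvement, with correlation r between improvement and the tendency to stay. The shift in the arm difference is then

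r × SD × [λ(p₁) − λ(p₂)], with λ(p) = φ(z_p)/(1 − p),

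where p₁ and p₂ are the proportions lost in each arm. The SD of 0.802 is the Day 71 figure, used for Day 11/12 as an assumption. The PP standard error is 0.802 × sqrt(2/114) = 0.106.

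- *Loss as in the earlier trial.* Protocol 2.3.2 gives 59 patients as 96.7% and 53 as 84.1%, so PP was 61 and 63. Table 9.1 gives 72 per arm in that trial's ITT set. Loss was 11/72 = 15.3% on active and 9/72 = 12.5% on placebo. λ = 0.279 and 0.235, a difference of 0.043. For r = 0.3 to 0.7 the shift is 0.010 to 0.024 points, or 0.10 to 0.23 SE. This assumes all the loss falls after Visit 2.
- *Assumed 30% v 20% loss.* λ = 0.497 and 0.350, a difference of 0.147. The shift is 0.035 to 0.082 points, or 0.3 to 0.8 SE.
- *Equal loss.* The shift is about 0.

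**The case against.** The strongest reply is that the remedy is already in the plan. Efficacy criteria are also analysed in ITT, which at Visit 2 is essentially the set proposed here, so the dispute is over which planned result is called main. That stands, and it limits the harm. A reader might infer that the Day 11/12 outcomes are thrown away; the documents do not support that, because only PP, and in part mITT, leaves them out. The safeguard is still weaker than it looks. Protocol 9.7.2 calls ITT inappropriate for judging efficacy. Protocol 11.8 removes patients with major deviations from the final efficacy analysis without limiting this to PP, as Protocol 9.3 does.

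Second, the PP rule may be meant for the primary criterion only. The sentence in 9.7.2 ties the proof of superiority to that criterion, and SAP 9 spells out main and additional sets only for the primary variable, naming none for the secondary endpoints. The text is less uniform than one would like, but the general wording in 9.7.2 and SAP 6 leaves PP as the governing rule.

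Third, two tempting extensions fail. Patients with a prohibited drug or a missed visit may still attend Visit 4; they leave PP because of the deviation, not because they never reach Day 71. And mITT does not share the PP condition in full, because it keeps patients with deviations who finish the course.

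Fourth, the point would disappear if ITT became the main set throughout. True, but it can be settled on its own, without reopening the choice for Day 71.

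**Conclusion.** The point holds as a modest one about secondary endpoints. Under the general rule, a complete Day 11/12 result can leave its main analysis because of a later event, and the stated reason for PP does not justify that. The number affected is 0 to 76 of 304, and the PP standard error is 1.00 to 1.15 times as large. A reader might take 76 patients and 15% as the expected cost; they are a ceiling that requires every loss to fall after Visit 2.

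Bias needs two conditions that the documents neither state nor exclude: later loss must depend on Day 11/12 status, and it must differ by arm. With the earlier trial's loss it is about 0.01 to 0.02 mRS points. The larger figure of 0.035 to 0.082 should not be read as a forecast, because the 10-point gap between arms behind it has no source in the documents. The correlations, the timing of loss and the use of the Day 71 SD are assumptions throughout.

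**What to change.** In Protocol 9.7.2 and SAP 11, add: *For all endpoints at the end of parenteral therapy, the main analysis set is all randomised patients with a Visit 2 assessment, whatever happens after Visit 2; the PP result is supportive.* Saying all endpoints rather than a number lets the sentence fit both the Protocol's seven and the SAP's six. Align the exclusion rule in Protocol 11.8 with it, and report N by visit in SAP Tables 3, 5 and 6, which show Visits 2 and 4 side by side. The Day 71 secondary endpoints stay as planned.

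The cost is wording: the Visit 2 data are already collected and the ITT analysis is already planned. There are two downsides. Some patients with deviations enter the main Day 11/12 analysis, and the same scale has different main sets at Visit 2 and Visit 4.

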9. STATISTICS

9.1. Calculation of sample size

The sample size calculation was based on the results of the Phase III clinical trial of Mexidol® [Multicentre randomized double-blind placebo-controlled parallel-group trial of the efficacy and safety of MEXIDOL® (solution for intravenous and intravenous administration / coated tablets) in long-term sequential therapy in patients with hemispheric ischaemic stroke in

the acute and early recovery periods - (EPICA)] dated 30.09.2016.

The trial plans to test the hypothesis of "superiority" of therapy with the investigational product vs. placebo therapy. The following indicator was chosen as the primary efficacy criterion: "The magnitude of change in the patient's **mRS** (Modified Rankin Scale) score at the end of therapy (Day 71) vs. baseline (in points)"

In the case of a superiority trial, the null hypothesis (H_0) and the alternative hypothesis (H_1) are formulated as follows:

$$H_0: \varepsilon = \mu_T - \mu_p \leq \delta, H_1: \varepsilon > \delta, \delta > 0, \text{ where}$$

- ε is the true difference between the value of the primary efficacy index (μ_T) in the group of patients taking the investigational product (T) and the value of the primary efficacy index (μ_p) in the group of patients taking placebo,
- δ - the boundary of "superiority" of therapy with the investigational product compared to placebo therapy by the primary efficacy indicator.

To prove superiority of therapy with an investigational product compared with placebo therapy, the lower bound of the 95% one-sided confidence interval (CI) for the difference in values of the primary efficacy criterion ($\mu_T - \mu_p$) must be greater than δ , where $\delta > 0$, i.e. CI must fall within the interval $(\delta, +\infty)$.

To calculate the sample size, data from the EPICA clinical trial were used for the ITT population (patients who received the investigational product or placebo at least once), as this population allows us to draw conclusions about the efficacy of the investigational therapy on the population closest to the patient population in real clinical practice. The results of the previously conducted EPICA clinical trial are summarized in Table 9.1.

Table 9.1. *Change in mRS score at the end of therapy relative to baseline [Visit 1 (Day 1) to Visit 5 (Day 67-71)] in patients enrolled in the ITT population.*

[μ - arithmetic mean; SD - standard deviation, DM - difference in mean averages]

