9.4. Dealing with dropped out, excluded patients and missing data

No missing data will be completed, missing data will not be taken into account when performing statistical analyses.

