9. Statistical evaluation of efficacy parameters and pharmacodynamic effects

Statistical processing of the data (case report forms of all sites) at the end of the trial will be carried out by staff not involved in the management of the patients participating in the trial, in order to create conditions for independent evaluation of the results obtained. The data will be processed in an electronic database using statistical programmes with the necessary functions (TIBCO® Statistica™ v.13 or higher and R v.3.6.2 or higher or other specialised software that determines the appropriate quality of the results obtained).

Descriptive statistics are provided for demographics, baseline values of indices, and values of efficacy and safety indicators at trial visits for the drugs being compared.

Interval (quantitative) data will be described using: arithmetic mean, standard deviation, median, lower (25%) and upper (75%) quartiles, minimum, maximum and coefficient of variation. Categorical (qualitative) data will be described using frequencies, percentages and/or fractions.

The results of quantitative variables evaluation whose distribution follows the law of normal distribution will be presented as $M \pm SD$, where M - mean and SD - standard deviation. The results of quantitative variables evaluation whose distribution does not follow the law of normal distribution will be presented as $Me [Q_1; Q_3]$, where Me - median and Q_1 and Q_3 - lower and upper quartiles.

The Shapiro-Wilk criterion will be applied to select parametric or non-parametric methods of analysis. When testing statistical hypotheses, parametric criteria will be used for indicators that have a normal distribution, and non-parametric criteria will be used for indicators with distribution other than normal. Demographic characteristics and descriptive statistics for baseline indicator values will be presented for the population of all randomized patients.

The primary efficacy variable will be analysed in the PP population (main), and in the ITT and mITT populations (additional). Confirmation of superiority of therapy with Mexidol® solution for intravenous and intramuscular injection, 50 mg/ml (RPC PHARMASOFT LLC, Russia) and Mexidol® FORTE 250 film-coated tablets, 250 mg (RPC PHARMASOFT LLC, Russia) over placebo therapy will be based on the magnitude of change in the patient's mRS (Modified Rankin Scale) scores at the end of the therapy (Day 71) vs. baseline (in scores).

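### Superiority is to be proved in per-protocol completers for a reason that does not support that choice; the interim text names all 304 randomised patients instead, and the supporting ITT analysis is available-case

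*Protocol*

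**What the plan says.** **Primary set.** Protocol 9.7.2 and SAP 6, 9 and 11 place the proof of superiority in PP. SAP 9: "The primary efficacy variable will be analysed in the PP population (main), and in the ITT and mITT populations (additional". SAP 11 defines the set: "The PP (Per protocol) population will include patients who completed the trial in accordance with the Protocol". Protocol 9.7.2 justifies it by the effective standard therapy given in both arms: "Therefore, the use of the ITT population for a more conservative assessment of ongoing therapy is inappropriate, as this approach markedly offsets the clinical effects".

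**Sizing.** Protocol 9.1 takes its inputs from EPICA's ITT data because "this population allows us to draw conclusions about the efficacy of the investigational therapy on the population closest to the patient population" seen in practice. It randomises 304 patients, of whom "at least 228 should complete the trial according to the Protocol".

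**A different set for the same test.** Protocol 9.1 and 9.9 and SAP 12 run the primary-endpoint analysis, and the one-sided interval that follows from it, on all 304 randomised patients.

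**Supporting sets.** ITT is all randomised patients. For mITT, Protocol 9.6 says: "The mITT (modified Intent-to-treat) population will include patients who have completed the full course of therapy". It is therefore another completer set.

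**Missing data.** Protocol 9.4: "No missing data will be completed, missing data will not be taken into account when performing statistical analyses". SAP 11 also rules out imputation.

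**Withdrawals and deaths.** Protocol 6.1 and 6.2 give early withdrawals a closing visit with the Visit 4 procedures, mRS included. The mRS form in Appendix 2 scores death as 6. No text links either score to the primary endpoint.

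**The concern.** Randomisation protects a comparison of everyone randomised. Under Protocol 5.3 patients leave the trial for recurrent stroke, loss of contact, adverse events that the investigator judges make continuing dangerous, or an investigator or sponsor decision after a significant deviation. Protocol 11.8 adds missed visits and poor adherence as major deviations. Several of these can depend on how the patient is doing or on treatment. A test in those who remain does not compare the randomised arms, and the bias can go either way.

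The stated reason does not help. Standard therapy is common to both arms in PP and in ITT, and the placebo control already accounts for it. The protocol itself treats ITT as the more conservative set and then sets it aside for a superiority claim, although its planning inputs are ITT values.

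The supporting ITT analysis is a partial check. It brings back completers with deviations, provided Protocol 9.3 governs (removal from PP only) and not 11.8 (removal from the final efficacy analysis). It does not bring back patients with no end-of-therapy score, because those are ignored.

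**Working it through.** **Inputs.** From Protocol 9.1: expected difference 0.292, margin 0.027, SD 0.802, one-sided alpha 0.05, power 80%, 1:1 allocation. From Protocol 2.3.2 (EPICA): 150 randomised, 141 completed, 124 in the efficacy set. From Table 9.1: 144 in EPICA's ITT table.

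**The plan's own figure.** n per arm = 2 × (1.6449 + 0.8416)² × 0.802² / (0.292 − 0.027)² = 113.25, rounded up to 114, so 228 in all; 228 / 0.75 = 304. This reproduces. The issue is the analysis set, not the arithmetic.

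**Who may be left out.** 1 − 228/304 = 25%, or 76 patients. In EPICA 26/150 = 17.3% were outside the efficacy set: 17 were completers, 9 (6%) had dropped out.

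**Does EPICA show ITT diluting the effect?** ITT difference: 2.278 − 1.986 = 0.292. PP difference: 2.3 − 2.0 = 0.3. The PP means are rounded to one decimal, so that difference could lie between 0.2 and 0.4. The figures show neither marked dilution in ITT nor inflation in PP.

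**Illustrated false-claim rate in PP, zero-effect drug, 114 per arm.** SE = 0.802 × √(2/114) = 0.1062. If excluded patients improve g points less than the rest, and the active arm excludes a share d more than placebo, the PP difference shifts by b = d × g. Rate = 1 − Φ(1.645 − (b − 0.027)/0.1062). The values of g and d are assumptions.

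| Imbalance d | g | Rate |
|---|---|---|
| 0 | any | 2.9% |
| 2.67 points | 0.5 | 3.8% |
| 2.67 points | 1 | 5.0% |
| 2.67 points | 2 | 8.1% |
| 5 points | 1 | 7.7% |
| 2.67 points, reversed | 1 | 1.6% |

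The 2.67 points come from EPICA's PP arms, 59/0.967 = 61 and 53/0.841 = 63, if 75 were randomised per arm (14/75 − 12/75). The documents do not state that split.

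**Tipping points.** At 152 per arm SE = 0.802 × √(2/152) = 0.0920, and success needs 0.027 + 1.645 × 0.0920 = 0.178. If analysed patients show 0.292 and a fraction f is not analysed, the all-randomised difference falls below 0.178 when the unanalysed active patients do worse than the unanalysed placebo patients by ((1 − f) × 0.292 − 0.178)/f:

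- f = 25%: 0.16 points
- f = 17.3%: 0.36 points
- f = 6%: 1.6 points, or 1.6/0.802 = 2.0 SD

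The first two describe the gap between PP and all randomised patients, much of which the ITT analysis would show. The third describes the part it cannot show.

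**Power with ITT primary, 152 per arm.** Power = Φ((0.292 × (1 − x) − 0.027)/0.0920 − 1.645), where a share x contributes no difference:

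- x = 0: 89% (84% at alpha 0.0294)
- x = 6%: 85%
- x = 25%: 67%

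**Deaths scored 6.** Assume mortality p, equal by arm. Difference = (1 − p) × 0.292. Variance = (1 − p) × 0.802² + p(1 − p) × (arm mean − (baseline − 6))², averaged over arm means 2.278 and 1.986. EPICA's end scores and changes imply a baseline of 1.1 + 2.3 = 3.4 and 1.5 + 2.0 = 3.5, about 3.45.

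| p | SD | Difference | Power | Power, baseline 3 to 5 |
|---|---|---|---|---|
| 2% | 1.030 | 0.286 | 71% | 68–80% |
| 5% | 1.286 | 0.277 | 52% | 48–68% |

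**The case against.** The strongest reply has four parts.

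1. *There is a missing-data rule.* Correct. A reader might infer that patients without a Day 71 mRS are left without any rule. Protocol 9.4 and SAP 11 state one: no imputation, missing values ignored. What stands is that this rule turns ITT into an available-case analysis, with no sensitivity analysis planned for missing outcomes.

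2. *The time point is settled.* Largely correct. Protocol 6.3.11 schedules mRS at Visits 0, 2 and 4, SAP Table 3 takes Visit 4 against Visit 0, and Visit 4 is Day 71. The natural reading is that the closing visit of an early withdrawal is a separate assessment. It is not written down, and the treatment of deaths is not addressed at all.

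3. *PP is not the only confirmatory set.* Also correct as far as it goes, since the interim text names all 304 randomised patients. That does not defend 9.7.2; the documents conflict on the primary set.

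4. *No harm is shown.* A reader might infer that PP inflates the effect or the error rate. The documents do not support that. EPICA's two differences are close, the illustrated rate exceeds 5% only under assumed gaps or imbalances and falls if the imbalance reverses, and at EPICA's 6% dropout the unseen patients would have to differ by about 2 SD to overturn the result. The objection to PP rests on validity of the comparison, not on a predicted false positive.

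**Conclusion.** The point holds. The documents place the superiority claim in a set selected after randomisation, for a reason that does not bear on the choice, and they contradict themselves by naming all 304 randomised patients for the same decision. Up to 25% of randomised patients may fall outside PP. The size and direction of bias cannot be known from the documents.

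The ITT analysis would expose the part due to completers with deviations. It would not expose the part due to patients without an end-of-therapy score; at EPICA-like dropout that part is unlikely to decide the result.

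The allowance and the power on planning inputs follow from the protocol. The false-claim rates rest on assumed gaps and imbalances. The 2% and 5% mortality rates are assumptions, since EPICA reported no deaths. The baseline of 3.45 is EPICA's, and this trial's NIHSS entry range (9 to 15) differs from EPICA's (5 to 20), hence the range over baseline 3 to 5.

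**What to change.** 1. Make ITT (all randomised, as randomised) the primary set for the superiority test in Protocol 9.7.2 and SAP 6, 9 and 11. Keep PP as a sensitivity analysis. Align Protocol 9.1 and 9.9 and SAP 12 with this.
2. For the primary endpoint, replace the rule of ignoring missing values. Score death as 6, as on the trial's own form. State whether the early-withdrawal mRS is used. Prespecify one method for a missing Day 71 mRS that draws on Visits 0 and 2, with a tipping-point analysis. The choice of method is the sponsor's.
3. Make Protocol 5.4.4 (undosed withdrawals left out) and 11.8 (major deviators left out) consistent with 9.6 and 9.3.
4. Restate power for the set and scoring rule chosen.

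**Cost.** Wording in both documents and analysis of data already scheduled; no new visit. The estimate may be less favourable and the stated power may be lower, as shown above. A reader might infer that the trial must enrol more patients. That is not asked for: the change is to report the power honestly.
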